9.5.4.2. Sensitivity Analysis

A sensitivity analysis may be performed to assess the primary estimand using mixed-effects model for repeated measures (MMRM) as a different missing data handling approach. The MMRM model will include treatment and stratification factors of migraine type (CM vs EM) and preventive medication use as fixed factors, as well as treatment-by-month interaction effects, and baseline number of migraine days as a covariate with an unstructured covariance matrix. The 12-week monthly average number of migraine days will be estimated by the LS means of the overall treatment effect over 3 months.

An additional sensitivity analysis may be conducted to assess a different estimand, ie, treatment effects due to initially randomized treatment as actually taken. For patients who early terminate from study drugs in the monthly dosing regimen group or start a rescue medication, observations collected more than 4 weeks after the last dose or after starting a rescue medication will be treated as missing and will not be used in the calculation of monthly average number of migraine days.

Finally, the primary analysis will be repeated in the ITT analysis set (in case there is a 10% difference in patient count in any treatment group) and PP analysis set.

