2.4. Sample Size and Power Considerations

Using study data from 2 completed Phase 3 US pivotal studies in migraine, it is estimated that 163 completers per treatment group (ie, combined fremanezumab groups and placebo group) will provide at least 90% power to detect the assumed treatment difference at a significance level of 0.05. Assuming a 12% discontinuation rate, approximately 372 patients will be randomized in this study (93 patients in each fremanezumab treatment group and 186 patients in the placebo group). The primary efficacy analysis will consider all fremanezumab-treated patients as 1 group.

To ensure adequate representation of patients with both migraine types (EM and CM), the enrollment minimum of either migraine type is 30%. In addition, primary efficacy analysis will be stratified by EM and CM, and subgroup analysis for EM and CM will be conducted.

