3.2. Modified Intent-to-Treat Analysis Sets

The double-blind modified intent-to-treat (mITT) analysis set is a subset of the ITT analysis set including only patients who receive at least 1 dose of IMP and have at least 10 days of post baseline efficacy assessment on the primary endpoint. The double-blind mITT analysis set will be used for the primary estimand analysis and all of its sensitivity analyses. The open-label mITT analysis set is a subset of the ITT analysis set including only patients who receive at least 1 dose of IMP during the open-label treatment period and have at least 10 days of post baseline diary entries during the open-label treatment period.

In the mITT analysis sets, treatment will be assigned based on the treatment to which patients were randomized, regardless of which treatment they actually received.

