4.3. Handling Withdrawals and Missing Data

If a patient has ≥ 10 days of electronic headache diary data after the 1st dose of the study drug, his/her monthly average number of days/hours of efficacy variables *during the 12-week double blind period* will be prorated to **28** days. Similarly, if a patient has ≥ 10 days of electronic headache diary data after the 4th dose of the study drug, his/her monthly average number of days/hours of efficacy variables *during the 12-week open label period* will be prorated to **28** days.

Patients who have <10 days of electronic headache diary data for the primary endpoint during the double blind period will be excluded from the double blind mITT analysis set. Patients who

have <10 days of electronic headache diary data during the open label period will be excluded from the open label mITT analysis set.

A patient's monthly number of days of efficacy variables *during the 4-week period* after each dose of study drug will be calculated. If a patient has missing diary days in a month, the following method will be used to handle the missing data.

- If the patient has 10 or more days of electronic headache diary data for a month, the monthly number of days/hours of efficacy variables will be prorated to **28** days for that month.
- If the patient has less than 10 days of electronic headache diary data for a month, the monthly number of days/hours of efficacy variables will be considered as missing.

A sensitivity analysis will be performed to assess the primary estimand using mixed-effects model for repeated measures (MMRM) as a different missing data handling approach. The methods will be described in detail in Section 6.2.3.1.

Multiple imputation (MI) method will be applied on the primary variable as sensitivity analyses. The methods will be described in detail in Section 6.2.3.2.

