6.2.2. Primary Analysis of the Primary Estimand

The hypothesis testing for the primary analysis is:

 $H_o: \delta_1 = \delta_2$ vs $H_a: \delta_1 \neq \delta_2$

where δ_1 and δ_2 are the parameters of mean change from baseline in the monthly average number of migraine days during the 12-week period after the 1st dose of IMP for the combined TEV-48125 treatment groups and the placebo group respectively.

An analysis of covariance (ANCOVA) will be performed, including treatment (combined TEV-48125 groups vs. placebo) and stratification factors (as randomized) of migraine type (CM vs EM) and baseline preventive medication use (yes vs no) as fixed factors, as well as baseline number of migraine days as a covariate in the model. For the individual treatment groups (combined TEV-48125 groups and placebo) the least square (LS) mean, standard error (SE) and corresponding 95% confidence interval will be presented. For the treatment difference (combined TEV-48125 groups - placebo) the LS mean, SE, corresponding 95% confidence interval and p-value for comparison will be presented.

The statistical test will be two-sided at the alpha = 0.05 level of significance. Model fitting assumptions will be investigated.

Example SAS code is provided in Appendix D.

A hierarchical procedure will be used to control the type 1 error rate, as described in Section 7.

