6.2.3.2. Analysis with Multiple Imputation Method

Multiple imputation (MI) method will be applied to impute the monthly missing data assuming a missing not at random (MNAR) mechanism. The data will be processed by the following steps.

- If a patient has <10 days of electronic headache diary device data in a month, that month's value will be considered missing before the MI procedure.
- For the patients in the active treatment groups who are early terminated with reasons of treatment-related adverse event or lack of efficacy, they will be assigned to placebo group so their missing values will be imputed using data from the placebo treated patients.
- Run SAS PROC MI procedure to create 100 complete datasets.
- Within each imputed data set, for a patient who has partial, say X days (X<28), electronic headache diary device data in a month, the monthly value will be replaced by ∑(oberseved migraine days) + (28 X) * imputed value/28
- The monthly average number of migraine days *during the 12-week period* after the 1st dose of study drug will be the average of month 1, month 2, and month 3 values.

Each dataset will be analyzed using the same ANCOVA model as described in Section 6.2.2. The LS means and standard errors from each analysis will be output to a SAS data set. SAS MIANALYZE procedure will be used to generate the final LS means (\pm SE) for the treatment groups and the treatment difference (TEV-48125 - placebo) as well as p-values associated with

treatment differences. The 95% confidence intervals for the treatment difference will also be constructed.

The output dataset will contain the estimate of the mean difference and the standard error of the estimate from each of the 100 datasets. SAS procedure, PROC MIANALYZE, will be used to generate an overall p-value and 95% CI for the treatment difference.

This sensitivity analysis will be performed on the ITT analysis set.

Example SAS code is provided in Appendix D.

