Patient receives the wrong IMP due to medication errors	Treatment policy ¹
Patient receives a rescue medication due to worsening symptoms	Hypothetical: For patients who start a rescue medication, observations collected after starting rescue medication will be treated as missing. In formula (1) an average is taken so these values which are left missing due to starting rescue medication will be replaced with the average for that month of those in the same treatment group who do not start rescue medication.

¹Treatment policy: if observations are collected after the occurrences of the ICEs, the observations will be included in the calculation of the primary endpoint for the primary analysis.

A third supplementary estimand will estimate treatment effect in the population that comprises the patients in the ITT analysis set. The estimand is the difference in adjusted means between fremanezumab group and placebo group for the change from baseline in the monthly average number of migraine days during the 12-week period after the 1st dose of IMP where the ICEs are handled as per Table 1.

Finally, a fourth supplementary estimand will estimate the treatment effect in the population that comprises the patients in the PP analysis set. The estimand is the difference in adjusted means between fremanezumab group and placebo group for the change from baseline in the monthly average number of migraine days during the 12-week period after the 1st dose of IMP where the relevant ICE is handled as per Table 4.

Table 4: Intercurrent Event Strategies: 4 th Supplementary Estimand	

Intercurrent event	Strategy
Patient receives a rescue medication due to	Treatment policy ¹
worsening symptoms	

¹Treatment policy: if observations are collected after the occurrences of the ICEs, the observations will be included in the calculation of the primary endpoint for the primary analysis.

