6.2.5. Analysis of the Supplementary Estimands

The supplementary estimands will be analyzed using the same methods as the primary estimand, as detailed in Section 6.2.2.

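### The ITT supplementary analysis reuses the observed-data ANCOVA and so largely or wholly repeats the mITT result, and the SAP assigns the multiple imputation to two different analysis sets

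*SAP*

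**What the plan says.** - **Sets.** ITT is all randomised patients (SAP 3.1). The double-blind mITT set also requires at least one dose and at least 10 days of post-baseline data (SAP 3.2). The same section adds: "The double-blind mITT analysis set will be used for the primary estimand analysis and all of its sensitivity analyses".
- **ITT estimand.** SAP 6.2.4: "A third supplementary estimand will estimate treatment effect in the population that comprises the patients in the ITT analysis set", with the treatment-policy strategies of Table 1. These use data after an intercurrent event only where such data were collected.
- **Method.** SAP 6.2.5: "The supplementary estimands will be analyzed using the same methods as the primary estimand", with reference to 6.2.2. That is an ANCOVA with one change value per patient; the sample code in Appendix D has no imputation step. Protocol 9.3.1 makes observed data the default.
- **Ten-day rule.** SAP 4.3 prorates the 12-week average when a patient has 10 or more diary days. It then says "Patients who have <10 days of electronic headache diary data for the primary endpoint during the double blind period will be excluded" from the double-blind mITT set. Formula (1) in SAP 6.1 divides by the recorded days and sets no minimum.
- **Multiple imputation.** SAP 6.2.3.2, listed among the sensitivity analyses of the primary estimand, imputes months 1 to 3 under a missing-not-at-random assumption and says: "This sensitivity analysis will be performed on the ITT analysis set".
- **Protocol.** Section 9.5.4.2 repeats the primary analysis in ITT only "in case there is a 10% difference in patient count in any treatment group". SAP 6.2.4 drops that condition, and the SAP's introduction gives the SAP precedence.

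**The concern.** An ITT analysis beside an mITT primary should show whether the result survives when the excluded patients are put back. Here the method needs an observed 12-week value, which is what most or all of the excluded patients lack. Agreement between the two rows would then follow largely from the method, yet could be read as robustness.

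The analysis-set conflict adds a second difficulty. If the imputation runs on ITT, comparing it with the primary changes the population and the missing-data assumption together. A difference could not be attributed to either one.

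**Working it through.** **1. The plan's own figure.** Inputs: "The statistical test will be two-sided at the alpha = 0.05 level of significance" (SAP 6.2.2) and "163 completers per treatment group (ie, combined fremanezumab groups and placebo group) will provide at least 90% power" (SAP 2.4). The assumed difference and SD are not legible in the current sample-size text. The amendment log (Protocol 16.4) shows 1.6 and 4.45 days, used here as assumptions.
- n per group = 2 × (1.960 + 1.282)² × (4.45/1.6)² = 162.6, so 163. Power at 163 is 90.1%.
- 163/0.88 = 185.2, so 186 per group and 372 in total.

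The stated figures reproduce. They do not bear on this point except to set the scale.

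**2. Who can be added, and whether the ANCOVA can use them.**

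| Patients in ITT but not mITT | 12-week value under SAP 6.2.2 |
|---|---|
| Never dosed | None: the endpoint period and the diary windows (SAP 4.4) start at the first dose |
| Dosed, no diary days | None: formula (1) has a zero denominator |
| Dosed, 1 to 9 diary days | None if the 4.3 proration rule governs; a noisy value if formula (1) is applied as written |

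For monthly values, SAP 4.3 says outright that fewer than 10 days is missing. For the 12-week average it states only exclusion from mITT. The third row is therefore ambiguous.

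**3. Simulation of the two readings.** 1,000 replicates, 372 patients, 1:1, the 6.2.2 model. Assumed: true difference 1.6 days, residual SD 4.2, 45% chronic migraine, 25% on preventive medication, baseline means 16 (chronic) and 9 (episodic). Between 1% and 10% of patients (about 4 to 37) fall outside mITT, half with no diary days and half with 1 to 9, unrelated to outcome.

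| Outside mITT | ITT minus mITT, fewer than 10 days missing | Mean absolute shift, 1 to 9 days prorated | SE of the estimate |
|---|---|---|---|
| 1% | 0.000 in every replicate | 0.04 days | 0.44 |
| 2% | 0.000 | 0.06 | 0.44 |
| 5% | 0.000 | 0.10 | 0.45 |
| 10% | 0.000 | 0.14 | 0.46 |

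The zeros follow from the first reading, because the same records enter both models. In the third column the patients with no diary data are still absent.

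**4. Possible size.** Suppose a share q of the fremanezumab group is lost with no benefit. The ITT effect is then (1 − q) × Δ while the row shows about Δ, an overstatement of q × Δ. With Δ = 1.6 and SE = 4.45 × √(2/186) = 0.46 days:
- q = 2%: 0.03 days, 0.07 SE
- q = 5%: 0.08 days, 0.17 SE
- q = 10%: 0.16 days, 0.35 SE

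**5. Would the imputation as written repair this?** Not by itself. SAP 6.2.3.2 moves to the placebo model only active patients who terminated for a treatment-related adverse event or lack of efficacy. All others, including never-dosed patients, are imputed under their own arm. In the scenario of step 4, such fremanezumab patients would receive fremanezumab-like months and the estimate would stay near Δ. Imputed from the placebo model, it would move towards (1 − q) × Δ, for example 0.95 × 1.6 = 1.52 days at q = 5%.

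**The case against.** Five points can be made against the concern.

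- **The rows need not be identical.** Formula (1) has no minimum, so patients with 1 to 9 days may enter the ITT row. This stands: a reader might infer that the two results must agree exactly, and the text does not settle that. Patients with no diary data are lost on either reading.
- **An ITT analysis that imputes is already planned.** Also true, so it would be wrong to infer that the SAP has no analysis retaining these patients. But the imputation is not the analysis assigned to the ITT estimand, and as written it fills most lost patients from their own arm.
- **Missing data are examined elsewhere.** The MMRM (SAP 6.2.3.1), on mITT under SAP 3.2, changes the missing-data handling with the population held fixed. This stands, but it does so only under missing at random.
- **The number is probably small.** Randomisation and first dose share visit 2, entry requires at least 21 baseline diary days, and patients who stop treatment are encouraged to continue assessments. This is persuasive, and the documents give no count against it.
- **The set conflict is only wording.** The specific section could be read as overriding the general one. However, SAP 14 presents the imputation as an added check on missing data and mentions no change of population.

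**Conclusion.** The point holds as a low-severity clarification. The planned ITT row wholly repeats the mITT result if fewer than 10 diary days means missing. It largely repeats it if 1 to 9 days are prorated, with an average shift of 0.04 to 0.14 days under the simulation's assumptions. In neither case is it independent evidence of robustness. SAP 3.2 and 6.2.3.2 also contradict each other on the set for the imputation.

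The overstatement of q × Δ is an illustration, not a forecast. It assumes no benefit in the lost fremanezumab patients, and q is unknown. A reader might take the protocol's 10% condition as the expected size, but the SAP makes the ITT estimand unconditional and nothing in the documents suggests that loss. Nor is the primary conclusion in doubt: this row carries no alpha, and the primary test and the testing sequence are untouched.

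**What to change.** 1. In SAP 6.2.5, analyse the third supplementary estimand with the 6.2.3.2 multiple imputation on the ITT set. Set TRTMI to placebo for never-dosed patients and for those with fewer than 10 diary days and no derivable value, instead of their own arm. Say how months 1 to 3 are defined for never-dosed patients, who have no first-dose date.
2. In SAP 6.2.3.2, run the missing-not-at-random sensitivity analysis on the double-blind mITT set, as SAP 3.2 states. It then differs from the primary only in the missing-data handling.
3. In SAP 4.3 or 6.1, state whether 1 to 9 diary days give a missing 12-week average.

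The cost is a few sentences, one extra run of existing code and a slightly more conservative ITT estimate. The changes should be made before unblinding at the first interim lock.

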6.2.5. Analysis of the Supplementary Estimands

The supplementary estimands will be analyzed using the same methods as the primary estimand, as detailed in Section 6.2.2.

6.2.6. Sub-Group Analyses

The primary analysis with ANCOVA method defined in Section 6.2.2 and MMRM analysis defined in Section 6.2.3.1 will also be applied to the following subgroups for the primary endpoint using a 'by' statement with the subgroup variable of interest. The subgroup variable will not be included in the model. Instead of the randomized stratification, the actual stratification will be used.

• Patients by migraine type (CM, EM)

6.3. Secondary Efficacy Endpoints and Analysis

6.3.1. Secondary Efficacy Estimands

The secondary estimands are as follows:

- The difference in adjusted means between fremanezumab group and placebo group in the population that comprises the patients in the mITT analysis set for the change from baseline in the number of migraine days during the 4-week period after the 1st dose of investigational medicinal product (IMP).
- The difference in adjusted means between fremanezumab group and placebo group in the population that comprises the patients in the mITT analysis set for the change from baseline in the monthly average number of days that any acute headache medications were used during the 12-week period after the 1st dose of IMP.
- The odds ratio of fremanezumab group with placebo group in the population that comprises the patients in the mITT analysis set n for the proportion of patients reaching at least 50% reduction in the monthly average number of migraine days during the 12-week period after the 1st dose of IMP.
- The difference in adjusted means between fremanezumab group and placebo group in the population that comprises the patients in the mITT analysis set for the change from baseline in the monthly average number of days with headache of at least moderate severity during the 12-week period after the 1st dose of IMP.

For all secondary estimands the ICEs will be handled as per Table 1.

For the first secondary efficacy estimand the baseline values will be derived using formula (3). The postbaseline values *during the 4-week period* will be derived using formula (2) and *the change* is calculated as *postbaseline – baseline value*. For the second and fourth secondary efficacy estimands the baseline values will be derived using formula (3). The postbaseline values *during the 12-week period* will be derived using formula (1), and *the change* is calculated as *postbaseline – baseline value*.

For the third secondary efficacy estimand the *percent reduction* will be calculated using formula (4). If a patient is early discontinued from the study, he/she will be counted as a non-responder.

6.3.2. Analysis of Secondary Efficacy Estimands

The first, second, and fourth secondary efficacy estimands which involve the difference in means between fremanezumab group and placebo group for change from baseline in efficacy variables will be analyzed using the same methods as the primary efficacy endpoint as detailed in Section 6.2.2 and 6.2.3.1 except the second secondary efficacy estimand model will include baseline number of days that any acute headache medications were used instead of baseline number of migraine days and the fourth secondary efficacy estimand model will include baseline number of days with headache of at least moderate severity instead of baseline number of migraine days.

The third secondary efficacy estimand involving the responder endpoint will be analyzed using logistic regression. The model will include treatment and stratification factors of migraine type (CM vs EM) and baseline preventive medication (yes vs no) use as fixed factors, as well as baseline number of migraine days as a covariate in the model. For the individual treatment groups (combined TEV-48125 groups and placebo) number and percent of responders and non-responders will be presented. For the treatment comparison (combined TEV-48125 groups with placebo) the odds ratio, 95% confidence interval for the odds ratio, and p-value for the treatment comparison will be presented.

Example SAS code is provided in Appendix D.

6.3.3. Supplementary Secondary Efficacy Estimands

The supplementary secondary efficacy estimands are identical to the secondary efficacy estimands but in the per-protocol (PP) analysis set. See Section 6.3.1 for the secondary efficacy estimands.

6.3.4. Analysis of Supplementary Secondary Efficacy Estimands

The analysis of the supplementary secondary efficacy estimands will be identical to the analysis of the secondary efficacy estimands. See Section 6.3.2 for details.

6.4. Other Efficacy Endpoints and Analysis

6.4.1. Exploratory Efficacy Endpoints

Placebo-Controlled Study–Migraine Study TV48125-CNS-30088

6.4.2. Analysis of Exploratory Endpoints

7. MULTIPLE COMPARISONS AND MULTIPLICITY

A fixed-sequence, hierarchical testing procedure will be implemented to control the type 1 error rate at 0.05 for formal hypothesis testing of the secondary endpoints at the end of the doubleblind period (i.e., 1st interim). Upon the success of the primary analysis, the first secondary endpoint in the sequence will be tested at a significance level of 0.05, and a p-value ≤ 0.05 will be interpreted inferentially. The process will continue following the order of the sequence until a point when the test for the efficacy endpoint fails, ie, 2-sided p-value ≥ 0.05 . Subsequently, no further test results will be interpreted inferentially. The sequence of testing upon the success of the primary analysis will be as follows:

- 1. mean change from baseline in the number of migraine days during the 4-week period after the 1st dose of IMP
- 2. mean change from baseline in the monthly average number of days with headache of at least moderate severity during the 12-week period after the 1st dose of IMP
- proportion of patients reaching at least 50% reduction in the monthly average number of migraine days during the 12-week period after the 1st dose of IMP
- 4. mean change from baseline in the monthly average number of days that any acute headache medications were used during the 12-week period after the 1st dose of IMP

